12.6.1.4 Sub-group Analyses

Depending on the sample size available in subgroups, the primary endpoint will be tested in subgroups defined by

- ISUP grade group 1 and 2
- Number of biopsies within 12 months of Screening (1 and >1)
- ECOG performance status (0 and 1)
- Age by quartiles
- Race (white and non-white)
- Body mass index (BMI) (<18.5, 18.5-24.9, 25.0-29.9, and 30.0+)
- PSA density

- PSA by quartiles

12.6.2 Secondary Endpoints

12.6.2.1 Subsequent Prostate Cancer Treatment

The counts and proportions of subjects receiving subsequent prostate cancer treatment will be presented overall and by each type of cancer treatment and reason for therapy in both study treatment arms of the ITT and PP analysis sets. The exact 95% confidence intervals for the proportions will be presented as well.

Time to first subsequent prostate cancer treatment will be summarized using Kaplan-Meier (KM; [Kaplan and Meier 1958](#)) estimates for the ITT and PP analysis sets. The 25%, 50%, and 75% quartiles will be calculated and corresponding 95% CIs by the KM method. A KM plot for time to first subsequent prostate cancer treatment will be presented. The count and proportion of responding subjects who have an event or are censored will be summarized.

Subsequent prostate cancer treatment data will be provided in a listing.

12.6.2.2 PROs

For each PRO total score and pooled domain score or sub-score defined in [Section 8.1.3](#), actual values at baseline and change from baseline at 12, 24, and 36 months visits post randomization will be summarized in the ITT and PP analysis sets in each treatment arm. The best change within 36 months post-baseline will be summarized and compared between the arms. The responses to individual question items will not be summarized except for the EPIC-CP overall urinary function question, which will be presented at baseline and its shift change presented at post-randomization.

To assess potential missing individual items in each PRO questionnaire, a sensitivity analysis in the ITT analysis set will be conducted to calculate total scores and pooled domain scores by summing up all available individual items regardless of any missing individual score.

PRO results will be provided in a listing.

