8.1.3.1 Memorial Anxiety Scale for Prostate Cancer (MAX-PC)

Per the MAX-PC ([Appendix 3](#)), there are 18 questions designed to better understand how subjects cope with aspects of their treatment for prostate cancer and the medical tests frequently involved in their care. Responses to the items have 4 possible integer scores ranging from 0 (Not at all) to 3 (Often), so that higher scores reflect worse symptoms. The total MAX-PC score is the sum of the scores from the 18 items and ranges from 0 to 54. The total score is missing if any of the individual scores are missing.

The 18 items are categorized into subscales of Prostate Cancer Anxiety (items 1-11), PSA Anxiety (items 12-14), and Fear of Recurrence (items 15-18). The score for each subscale is the sum of the scores from the items within each subscale so that subscale scores range from 0 to 33, from 0 to 9, and from 0 to 12, respectively. The score for each subscale is missing if any of the individual scores in the subscale is missing.

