8.1.3.2 Short Form 12 Health Survey (SF-12)

The Standard SF-12 ([Appendix 4](#)) captures the subject's views about their own functional health and well-being in the past 4 weeks in 12 items. There are eight health domains measured using the SF-12 as follows:

- General Health (GH) – question 1 with a range of 1-5
- Physical Functioning (PF) – questions 2 and 3 with a range of 1-3 each
- Role-Physical (RP) – questions 4 and 5 with a range of 1-2 each
- Role-Emotional (RE) – questions 6 and 7 with a range of 1-2 each
- Bodily Pain (BP) – question 8 with a range of 1-5
- Mental Health (MH) – questions 9 and 11 with a range of 1-6 each
- Vitality (VT) – question 10 with a range of 1-6
- Social Functioning (SF) – question 12 with a range of 1-5

The SF-12 responses will be scored using OPTUM® PRO CoRE software, version 1.4 or higher, producing scores for the 8 health domains and the physical component summary (PCS) and mental component summary (MCS). Higher scores reflect higher functioning and well-being. The SF-6D index, a health state classification measure scored from 0.0 (worst health state) to 1.0 (best health state), will be derived based on the SF-12.

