8.1.3.3 The Expanded Prostate Cancer Index Composite for Clinical Practice (EPIC-CP)

The EPIC-CP ([Appendix 5](#)) asks questions about the subject's health and symptoms in the last four weeks. There is one overall urinary function question with possible responses of No Problem, Very small problem, Small problem, Moderate problem, and Big problem. Additionally, there are 5 domains with 3 questions each and possible integer score responses ranging from 0 to 4 as follows:

- Urinary Incontinence Symptom Score – questions 2-4
- Urinary Irritation/Obstructive Symptom Score – questions 5a-5c
- Bowel Symptom Score – questions 6a-6c
- Sexual Symptom Score – questions 7-9
- Vitality/Hormonal Symptom Score – questions 10a-10c

The total score for each domain is the sum of the individual scores within the domain, i.e., the total scores in each domain range from 0 to 12 and higher scores reflect worse symptoms. The pooled scores from all domains, the sum of all domain total scores, range from 0 to 60 and capture the Overall Prostate Cancer Quality of Life Score. Scores will be set to missing if any of the individual scores are missing.

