8.1.3.4 International Prostate Symptom Score (I-PSS)

The I-PSS ([Appendix 6](#)) consists of 7 questions about urinary symptoms (scores range from 0 to 5 each) and one question about quality of life (score ranges from 0 to 6), with higher scores indicating worse symptoms. The total I-PSS score is the sum of the scores from questions 1 to 7 and ranges from 0 to 35. Scores will be set to missing if any of the individual scores are missing.

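### The PRO missing-item sensitivity analysis scores each blank as 0, so blanks after baseline read as improvement and the check cannot show robustness to missing items

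*SAP*

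**What the plan says.** In the main PRO analysis an incomplete scale is not scored. For MAX-PC (SAP 8.1.3.1), "The total score is missing if any of the individual scores are missing", and each subscale follows the same rule. For EPIC-CP (SAP 8.1.3.3), "Scores will be set to missing if any of the individual scores are missing"; the I-PSS section (8.1.3.4) repeats that sentence. SF-12 is handled differently (8.1.3.2): "The SF-12 responses will be scored using OPTUM® PRO CoRE software, version 1.4 or higher".

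SAP 12.6.2.2 then adds a check: "To assess potential missing individual items in each PRO questionnaire, a sensitivity analysis in the ITT analysis set will be conducted", and its rule is to "calculate total scores and pooled domain scores by summing up all available individual items regardless of any missing individual score". No proration, item imputation or minimum number of answered items is given.

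The scales affected are sums of items that start at 0. For I-PSS, "The total I-PSS score is the sum of the scores from questions 1 to 7 and ranges from 0 to 35", "with higher scores indicating worse symptoms". For EPIC-CP, "there are 5 domains with 3 questions each and possible integer score responses ranging from 0 to 4", and higher is again worse. MAX-PC has 18 items scored 0-3, with a total of 0-54.

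Two uses of the scores matter here. Change from baseline is summarized at 12, 24 and 36 months. The best change within 36 months, defined in SAP 8.1.3 as the most favorable change at any assessment, unscheduled visits included, is compared between arms.

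**The concern.** A sum over answered items equals the full sum with every blank set to 0. On I-PSS and EPIC-CP, and on MAX-PC items 1-14, 0 is the no-symptom answer. The analysis meant to test sensitivity to missing items therefore replaces exclusion with one fixed imputation at the floor of the scale, and the error is largest for the men with the most symptoms. The resulting scores are also off the stated ranges, which presuppose complete forms, yet they enter the same change-from-baseline calculation as complete scores.

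At stake is what the check can tell the reader. Agreement with the main PRO result would not show robustness, and disagreement could be produced by the scoring rule alone. The best-change comparison is the most exposed, because taking the most favorable visit picks out visits whose totals were lowered by blanks.

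**Working it through.** **Inputs.** Item counts and score ranges come from SAP 8.1.3.1, 8.1.3.3 and 8.1.3.4, the I-PSS severity bands from the printed form (SAP Appendix 6), and the scoring rule and the best-change comparison from SAP 12.6.2.2 and 8.1.3. The item-missing rate q is not in the documents; I assume 2%, 5% and 10%.

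**Stated ranges reproduced.**
- I-PSS: 7 x 5 = 35.
- EPIC-CP: 3 x 4 = 12 per domain, 5 x 12 = 60 overall.
- MAX-PC: 18 x 3 = 54.

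All match, and all require every item to be answered.

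**One form.** Error in the total = -(sum of the answers the man would have given to the blank items). Each blank costs 0 to 5 points on I-PSS and 0 to 4 on EPIC-CP, and none can raise the total.
- Stable I-PSS, 3 on every item: 7 x 3 = 21 (severe). Two blanks at follow-up give 5 x 3 = 15 (moderate), a change of -6 where the truth is 0. Proration gives 15/5 x 7 = 21.
- Stable I-PSS, 2 on every item: one blank gives 12 against 14, a change of -2.
- I-PSS total of 8 (moderate) with an item of 2 left blank: scored 6 (mild).
- Stable EPIC-CP, 2 on every item: one blank gives 28 against 30, a change of -2.

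**Mean change at one visit.** If blanks are unrelated to the answers and the true mean total T is stable, bias = -(q at follow-up - q at baseline) x T.
- Blanks at follow-up only, T = 14: -0.28, -0.70 and -1.40 at q = 2%, 5% and 10%. For T from 8 to 20 the range is -0.16 (0.02 x 8) to -2.0 (0.10 x 20).
- Blanks at baseline only: same size, opposite sign.
- Same q at both times: 0.

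**Best change over three visits.** Take a man with every I-PSS item truly 2 throughout, so true best change is 0. Let B be the number of blanks at baseline and M the largest number of blanks at any of the three follow-up visits, each visit's count being Binomial(7, q). Best change = -2(M - B), with mean -2(E[M] - 7q). E[M] is the sum over k = 0 to 6 of 1 - P(count ≤ k)³.

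| q | E[M] | 7q | Same q at all visits | Baseline complete |
|---|---|---|---|---|
| 2% | 0.370 | 0.14 | -0.46 | -0.74 |
| 5% | 0.799 | 0.35 | -0.90 | -1.60 |
| 10% | 1.360 | 0.70 | -1.32 | -2.72 |

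Simulation with 400,000 men gave the same values to within 0.01. The bias that cancels in the single-visit mean therefore remains in best change.

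**The case against.** The strongest reply is that the stakes are small. This is a sensitivity analysis of a secondary endpoint. The main MAX-PC, EPIC-CP and I-PSS scores are missing when any item is blank, so the rule does not touch them, and SAP 12.6.1.2 says one test of the primary endpoint decides the study. Protocol 8.7 has site staff review each completed questionnaire before the man leaves, which may keep blanks few. All of that stands; it limits the size of the problem but does not make the rule sound.

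Some stronger readings are tempting, and the documents do not support them:
- A reader might infer that the rule favors improvement in anyone who skips an item. It does not: a baseline blank reads as later worsening, a blank whose true answer was 0 causes no error, and equal missingness cancels in the mean change at one visit.
- A reader might infer that the arm with more surgery or radiation will look better because treated men skip sensitive items. Nothing in the documents says so. Under Protocol 6.8 treated men move to the Follow-up Phase, where PROs are collected six-monthly, so their later forms may not enter the 12-, 24- and 36-month summaries, although they could enter best change. Between-arm bias needs blanks or symptom levels to differ by arm. That is possible in an open-label trial but not documented.
- A reader might extend the no-symptom argument to all of MAX-PC. On the printed form, items 15-18 score 0 for strongly agree, the most anxious answer, so it holds for items 1-14 only.
- A reader might conclude that SF-12 will be summed item by item. The SAP defines no summed SF-12 total and assigns scoring to software. The reference to each questionnaire leaves the scope unclear, which one sentence can settle.

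**Conclusion.** The rule is wrong as written, with limited consequences. It scores each blank at the no-symptom end of I-PSS, EPIC-CP and MAX-PC items 1-14, so it cannot serve as a check on missing items. Per form the error is exact: 0-5 points per blank I-PSS item and 0-4 per blank EPIC-CP item, toward improvement if the blank is after baseline and toward worsening if it is at baseline.

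For group means the size depends on an item-missing rate that the documents do not give. With equal rates of 2-10% at all visits, the single-visit mean change is unbiased, but I-PSS best change is biased by about -0.5 to -1.3 points. Those figures assume true item scores steady at 2, three follow-up visits, blanks unrelated to the answers, and best change recalculated under this rule, which SAP 12.6.2.2 does not expressly say. They describe bias within an arm, not a difference between arms.

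**What to change.** Replace the sentence in SAP 12.6.2.2 with proration per scale or subscale, applied alike at baseline and follow-up: where at least half the items are answered, score = mean of answered items x number of items in the scale; otherwise missing. The minimum is then 4 of 7 items for I-PSS and 2 of 3 for an EPIC-CP domain, so an I-PSS with four blanks or an EPIC-CP domain with two blanks stays missing. Build the EPIC-CP overall score from the prorated domains and the MAX-PC total from the prorated subscales. State that SF-12 is excluded and keeps its software scoring.

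The half-answered threshold is a proposed convention, not something the documents supply; what matters is that a minimum is fixed in advance. The cost is SAP wording and a few lines of code. The small downside is that proration assumes a man's skipped items resemble those he answered in the same scale.

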12.7 Safety Analyses

12.7.1 Adverse Events

A summary of AEs, including the number and percentage of events reported, and the number and percentage of subjects

- reporting at least one AE,
- with at least one grade ≥ 3 AE,
- with at least one SAE,
- with at least one study drug related AE (probable or possibly related),
- with an AE leading to death

will be presented by study treatment arm in the Safety population. In the summary by worst National Cancer Institute Common Terminology Criteria for Adverse Events (NCI CTCAE) v5.0 grade, the AE with the highest or most severe grade will be counted when subjects have multiple AEs in a SOC or PT.

A breakdown of the number and percentage of subjects reporting each kind of AE above, categorized by SOC and PT, will be also presented. This breakdown will be sorted by PT within SOC. Note that counting will be by subject and not by event and subjects are only counted once within each SOC or PT. This breakdown will be repeated and sorted by descending frequency of PTs in the sipuleucel-T arm for subjects reporting at least one AE and subjects reporting at least one grade ≥ 3 AE. This breakdown will also be

repeated by worst CTCAE grade for subjects reporting at least one AE and subjects reporting at least one grade ≥ 3 AE, sorted by PT within SOC.

AEs occurred within 1 day after any leukapheresis will be summarized. Similarly, AEs occurred within 1 day after any infusion will be summarized.

Listings of AEs will also be presented.

12.7.2 Deaths and Serious Adverse Events

A summary and listing of deaths from all causes will be presented for all subjects randomized, overall and by study treatment arm. See [Section 12.7.1](#) for analyses of AEs that lead to death and SAEs.

12.7.3 Clinical Laboratory Parameters

The clinical laboratory parameters to be analyzed are listed in [Section 8.3.2](#). Actual values at each planned visit and change in values from baseline at each post-baseline planned visit will be summarized. All laboratory results over time will be presented in a listing, including reference ranges and indications of out of range values, and an assessment of clinical significance by the Investigator. Shift tables will be used to present change in grading status from baseline.

These analyses will be performed in the Safety population, overall and by study treatment arm.

12.7.4 Vital Signs

The vital signs to be analyzed are listed in [Section 8.4.4](#). Vital signs at each scheduled visit will be summarized along with the change from baseline to post-baseline visits. The body mass index (BMI) at each visit will also be computed using the formula $BMI = \text{weight (kg)} / (\text{height (m)})^2$ and summarized. A summary of abnormal vital signs will also be presented, where abnormal vital signs are systolic blood pressure >140 mmHg, diastolic blood pressure >90 mmHg, heart rate <60 beats/min or >100 beats/min, or temperature $>37.5^\circ\text{C}$.

A listing of vital signs over time will also be presented. These analyses will be performed in the Safety population, overall and by study treatment arm.

12.7.5 Methods for Handling Dropouts and Missing Data

Below are rules for imputing missing or partial dates for analyses of medical history, AEs, and concomitant medications. Though imputed for analyses, actual dates (missing or partial) will be reflected in listings. Otherwise, there will be no imputation of missing data values. Data on subjects who withdraw early will be summarized up until the time of withdrawal.

Missing or partial dates for medical history will be imputed as follows:

- If only the day is missing, it will be imputed with the 15th day of the month.
- If both the day and month are missing, the month and day will be imputed with July 1st.
- If the date is completely missing, no imputation will be performed.

Missing or partial dates for AEs and concomitant medications will be imputed as follows:

- Start Date
 - If only the day is missing and the month and year are the same as the month and year of the first dose date, then the day will be imputed with the day of the first dose date. Otherwise the day will be imputed with the first day of the event month.
 - If both the day and month are missing and the year is the same as the year of the first dose date, then they will be imputed with the month and day of the first dose date. Otherwise they will be imputed with the July 1st of event year.

- If the start date is completely missing, the date will be imputed with the first dose date.

If the stop date is complete and the imputed start date is after the stop date, then the imputed start date will be set to the stop date.

- Stop Date
 - If only the day is missing and the month and year are the same as the month and year of the study discontinuation date, then the day will be imputed with the day of the study discontinuation date. Otherwise the day will be imputed with the last day of the event month.
 - If both the day and month are missing and the year is the same as the year of the study discontinuation then they will be imputed with the month and day of the study discontinuation date. Otherwise they will be imputed with the December 31st.
 - If the stop date is completely missing, then it will be imputed with the study discontinuation date.

Note that stop date imputation will not be applied to ongoing AEs. If the imputed stop date is greater than last the contact date, then the imputed stop date will be set to last contact date.

13.0 Validation

Quality control procedures will be documented separately in the study-specific quality control plan.

Appendix 1 Glossary of Abbreviations

Glossary of Abbreviations:	
AE	Adverse event
ATC	Anatomic Therapeutic Classification
BICR	Blinded Independent Central Review
CRF	Case Report Form
CSR	Clinical Study Report
DMC	Data Monitoring Committee
DRE	Digital Rectal Examination
DSMB	Data Safety Monitoring Board
ECG	Electrocardiogram
ECOG	Eastern Cooperative Oncology Group
FFPE	Formalin-Fixed Paraffin-Embedded
H&E	Hematoxylin and Eosin
HE	Health Economics
IHC	Immunohistochemistry
IRT	Interactive Response Technology
ISUP	International Society of Urological Pathology
ITT	Intention-to-treat
IVRS	Interactive Voice Response System
PE	Physical Examination
PK	Pharmacokinetic
PP	Per Protocol
PRO	Patient-reported outcome
QoL	Quality of Life
SAP	Statistical Analysis Plan
SAE	Serious Adverse Event

Appendix 2 Tables, Figures, Listings, and Supportive SAS Output Appendices

Refer to DDCP1701-P1701X TFL Shells_v1.0.docm for the mock tables, figures, and listings described in this SAP.

Appendix 3 Memorial Anxiety Scale for Prostate Cancer (MAX-PC)

The Modified 18-Item Memorial Anxiety Scale for Prostate Cancer

YOUR FEELINGS ABOUT PROSTATE CANCER AND PROSTATE SPECIFIC ANTIGEN TESTS

We would like to better understand how patients cope with aspects of their treatment for prostate cancer and the medical tests frequently involved in their care.

I. Below is a list of comments made by men about prostate cancer. Please indicate by circling the number next to each item how frequently these comments were true for you *during the past week*; not at all, rarely, sometimes, often.

	Not at all	Rarely	Sometimes	Often
1. Any reference to prostate cancer brought up strong feelings in me.	0	1	2	3
2. Even though it's a good idea, I found that getting a PSA test scared me.	0	1	2	3
3. Whenever I heard about a friend or public figure with prostate cancer, I got more anxious about my having prostate cancer.	0	1	2	3
4. When I thought about having a PSA test, I got more anxious about my having prostate cancer.	0	1	2	3
5. Other things kept making me think about prostate cancer.	0	1	2	3
6. I felt kind of numb when I thought about prostate cancer.	0	1	2	3
7. I thought about prostate cancer even though I didn't mean to.	0	1	2	3
8. I had a lot of feelings about prostate cancer, but I didn't want to deal with them.	0	1	2	3
9. I had more trouble falling asleep because I couldn't get thoughts of prostate cancer out of my mind.	0	1	2	3
10. I was afraid that the results from my PSA test would show that my disease was getting worse.	0	1	2	3
11. Just hearing the words "prostate cancer" scared me.	0	1	2	3

II. For the next three questions, please indicate how frequently these situations have *EVER* been true for you.

	Not at all	Rarely	Sometimes	Often
12. I have been so anxious about my PSA test that I have thought about delaying it.	0	1	2	3
13. I have been so worried about my PSA test result that I have thought about asking my doctor to repeat it.	0	1	2	3
14. I have been so concerned about my PSA test result that I have thought about having the test repeated at another lab to make sure they were accurate.	0	1	2	3

III. Listed below are a number of statements concerning a person's beliefs about their own health. In thinking about the *past week*, please indicate how much you agree or disagree with each statement: strongly agree, agree, disagree, or strongly disagree. Please circle the number of your answer.

	Strongly agree	Agree	Disagree	Strongly disagree
15. Because cancer is unpredictable, I feel I cannot plan for the future.	0	1	2	3
16. My fear of having my cancer getting worse gets in the way of my enjoying life.	0	1	2	3
17. I am afraid of my cancer getting worse.	0	1	2	3
18. I am more nervous since I was diagnosed with prostate cancer	0	1	2	3

PSA: prostate specific antigen.

